Study Title: Coupler-Based Hearing-Aid Fitting Approach for Experienced Users

NCT02772757

ID: C1895-P

Principal Investigator: [name], Au.D., Ph.D.

April 30, 2015

The purpose of this study is to evaluate procedures designed to greatly improve the efficiency of hearing-aid delivery to experienced hearing-aid wearers. Specifically, the fitting accuracy and patient experience for two approaches that would not require additional direct patient contact will be compared to the current standard-of-care (SoC) approach in which *in situ* real-ear aided responses (REARs) measures are obtained. The proposed approaches use derived REAR hearing-aid fittings based on either (1) average-corrected or (2) individually-measured real-ear to coupler differences (RECDs) for fitting and verification of *replacement* amplification. The primary research aims are to determine:

- 1. if the *in situ* REARs differ from the derived REARs in the experimental groups and if the derived REARs in the experimental groups differ from the *in situ* REARs in the SoC group,
- 2. if fittings based on measured versus average-corrected RECD values differ in the experimental groups, and
- 3. if the subjective hearing-aid outcomes differ among the groups.

RESEARCH DESIGN AND METHODS

Design. A mixed model, repeated measure design will be used in the current study.

Participants. There will be three groups of participants. One group will serve as the active-control group and will receive the standard-of care 30-min appointment (SoC group). One experimental group will have the average-corrected (for venting) RECD (Exp-AVGc Group) incorporated during the RECD-based verification and the other experimental group will have the measured (with custom earmold) RECD (Exp-M Group) incorporated during verification. The two experimental groups will be mailed their replacement hearing aids *after* they are programmed and verified with RECD-based fittings. The participants will be randomly assigned to each group.

Inclusion Criteria: Participants will be included in the study if the following criteria are met:

- experienced BTE hearing-aid users who are obtaining replacement VA-issued BTE hearing aids coupled to a custom earmold that is simply an upgrade in model (e.g., 2010 Phonak Exeila 211 Art BTE upgrading to a 2014 Phonak Bolero Q90 BTE) with the same style earmold

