Session 3 (One-Month Post-Fitting). One month after the hearing-aid fitting, all groups will return to complete subjective outcome measures. The measures will be presented in random order. The COSI outcomes will be measured to determine if the hearing aids are meeting the patient-nominated goals. The SADL will be completed and the *Service and Cost* subscale will be of great interest due to the service-related items that may differentiate between groups. The DOSO will be used as it assesses hearing-aid outcomes in six domains. An exit survey (**Appendix 2**) also will be administered to gain insight into the perceptions related to service delivery, access, and convenience. In addition, *in situ* REARs will be obtained from all groups using the current programming from the replacement aids. These *in situ* REARs will allow within and between group comparisons regarding the hearing-aid function and determine the accuracy of the experimental fittings relative to the SoC fittings. The repeat *in situ* REAR measurements in the SoC group (i.e., Sessions 2 and 3) will serve to assess the inherent variability with *in situ* REAR measurements and

will facilitate interpretation of REAR data when comparing the accuracy of the *in situ* and derived REARs in the experimental groups.

Attrition. In our experience ([name] and [name]) with a multi-session (4 sessions over 6 months), hearing-aid clinical trial, we had a low local attrition rate of 8.7%. The primary reasons for withdrawal were due to personal reasons which included illness, moving out of state, and transportation issues during inclement weather (i.e., snow). Thus, we considered a conservative estimate of 15% attrition for the proposed multi-session study.

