Sample Size. Based on an expectation that REAR measurements should be within 2 dB on average across frequency, and an SD of 2, then 18 participants are needed for each group (total N = 54) assuming a power of at least β = .80 and *p* = .05. Considering 15% attrition, then 9 additional subjects will be needed (N = 63) resulting in 21 participants per group. Participants will be recruited from the Mountain Home VA audiology clinics. Last year, our clinic served 7,481 Veterans during 16,278 patient visits and dispensed 7,134 hearing aids. Also, based on the national average, it is estimated that ~50% of VA hearing aids dispensed are replacement hearing aids for experienced users. Thus, we anticipate no difficulty in recruiting the target sample at Mountain Home.

Data Analysis.

Specific Aim 1 and 2. A mixed-model analysis of variance (ANOVA) will be conducted. This analysis will examine differences (in dB SPL) for REAR (actual vs derived using average vs measured RECD) across frequency and ears within and between the groups. This analysis will determine (1) if the *in situ* REARs differ from the derived REARs in the experimental groups and if the derived REARs in the experimental groups differ from the *in situ* REARs in the SoC group (2) if coupler-derived REARs using average-corrected or measured RECDs differ; and (3) if the average-corrected RECD.

Specific Aim 3. A multivariate ANOVA will be conducted to examine group differences among the outcome measure subscales. A logistic regression also will be conducted to examine if the proportion of responses differ among the groups on the specific telephone and exit survey items of interest.

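### Does enrolling 63 (21 per group) fall short of the 18 evaluable per group at the planned 15% attrition?

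*Combined protocol and SAP*

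**What the plan says.** The Sample Size section of the combined protocol and SAP starts from the expectation that "REAR measurements should be within 2 dB on average across frequency, and an SD of 2". From this it concludes that "18 participants are needed for each group (total N = 54"), "assuming a power of at least β = .80 and *p* = .05". The .80 is evidently the power, although it is labelled β. The attrition step follows: "Considering 15% attrition, then 9 additional subjects will be needed (N = 63) resulting in 21 participants per group".

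The rate comes from the Attrition section. The team cites its own earlier four-session hearing-aid trial, in which 8.7% of local participants withdrew, and goes on: "we considered a conservative estimate of 15% attrition for the proposed multi-session study". Neither section gives the formula or the rounding rule that turns 54 into 63. Equal group sizes follow from the 21 per group; the Participants section says only that "The participants will be randomly assigned to each group".

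**The concern.** The usual way to allow for attrition is to divide the evaluable number by the retained fraction: 18/0.85 = 21.18, which rounds up to 22 per group. A frequent mistake is to multiply by one plus the rate instead. Here 18 × 1.15 = 20.7 and 54 × 1.15 = 62.1, which round up to exactly the plan's 21 and 63, so the plan looks like a case of that mistake.

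If so, the four figures in the paragraph (63 enrolled, 15% loss, 18 evaluable per group, power of at least .80) could not all hold together. The trial would then risk ending below its planned power at the attrition rate it says it has allowed for.

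**Working it through.** **Inputs.** Sample Size section: 18 per group, 54 in total, difference 2 dB, SD 2 dB, power .80, significance level .05, 63 enrolled, 21 per group. Attrition section: 15% planned, 8.7% observed earlier. The plan does not name the test behind the 18, so two readings are carried through. Both compare two independent groups.

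**1. The base figure of 18.**
- Two-sided t-test for a 2 dB difference at .05: the solution is 16.7, so 17 per group. Power is 0.807 at 17 and 0.830 at 18.
- Equivalence by two one-sided tests (margin 2 dB, true difference zero, .05 each side): power is 0.773 at 17 and 0.805 at 18, so 18 is the smallest adequate number.

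The stated 18 is therefore matched exactly by the second reading and to within one participant by the first.

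**2. The step from 18 to 21.** Several routes arrive at the plan's figure:
- 18 × 1.15 = 20.7, rounded up: 21.
- 18/0.85 = 21.18, rounded to nearest: 21.
- 15% of 63 = 9.45, taken as 9 whole people: 63 − 9 = 54.

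The documents do not say which was used. Rounding up after division gives 22 per group (66 in total). On the total alone, 54/0.85 = 63.53 gives 64, which does not split equally into three.

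**3. The size of the shortfall at 15%.**
- Per group: 21 × 0.85 = 17.85; 18 − 17.85 = 0.15.
- Whole trial: 63 × 0.85 = 53.55; 54 − 53.55 = 0.45.
- Attrition covered exactly: 3/21 = 9/63 = 14.3%.

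**4. What it does to power.**

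| Completers per group | Two-sided t-test, 2 dB | Equivalence, margin 2 dB |
|---|---|---|
| 18 | 0.830 | 0.805 |
| 17.85 | 0.827 | 0.800 |
| 17 | 0.807 | 0.773 |

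At the expected number of completers, both readings still give .80.

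**5. At the attrition seen before.** 21 × (1 − 0.087) = 19.2 per group, above 18.

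**6. Chance variation.** Suppose each participant is lost independently with probability 0.15. The chance that a group ends below 18 is 39% with 21 enrolled and 23% with 22. The chance that all three groups reach 18 is 23% with 21 enrolled and 46% with 22.

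**The case for a change.** The best argument for acting is that participants are lost whole. A group cannot end with 17.85; it ends with 18 or 17. The equivalence reading is the one that returns 18 exactly, and it fits the plan's wording about being within 2 dB. Under that reading 18 has almost no slack, and a group of 17 has power 0.773, below the stated minimum. With 21 enrolled and a true 15% loss, a group falls below 18 with probability 39%. A one-sentence correction would cost nothing and would make the paragraph agree with its own inputs.

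The arithmetic in that argument is right, and so is the statement that 21 per group covers 14.3% rather than 15%. Its force is limited in three ways.

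- The equivalence test is an inference. The Data Analysis section specifies a mixed-model analysis of variance that asks whether the responses differ, and for a test of difference the power at 17 is still 0.807.
- The 39% is mostly ordinary variation in who drops out. At 22 per group it is still 23%, and all three groups reach 18 less than half the time. An allowance based on the expected loss does not guarantee the target in every group, whichever formula produces it.
- The difference between 14.3% and 15% is finer than a planning guess can support, especially one deliberately set above the observed 8.7%.

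**Conclusion.** No change follows. The stated figures disagree by a rounding remainder: 0.15 participant per group and 0.45 in the trial, equivalent to covering 14.3% attrition instead of 15%. The use of a wrong multiplier is not shown, since dividing by 0.85 and rounding to the nearest whole number gives the same 21. The stated power of at least .80 survives at the expected 17.85 completers under both readings, narrowly for equivalence (0.800) and with some room for a test of difference (0.827).

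Restating the tolerance as nine losses, or about 14%, would be marginally more exact. It would leave enrolment, analysis and interpretation as they are.

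The conclusion assumes a comparison of two independent groups with the plan's own 2 dB difference and SD of 2 dB, and that attrition does not run well above 15%. It concerns only the attrition step and does not judge whether 2 dB and SD 2 are the right planning values.

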- no more than a moderate sensorineural hearing loss (defined as < 60 dB HL pure-tone average at 500, 1000, and 2000 Hz AU)
- ability to read and write in English as determined by reading a few sentences from the consent document aloud so that self-report measures can be completed

Exclusion Criteria: Participants will be excluded if any of the following criteria are true:

- outer or middle ear pathology as determined by otoscopy, immittance, and/or audiometric testing (e.g., conductive or mixed losses)
- lack of phone or non-use of the phone as the participants will be required to conduct a telephone interview after they obtain their replacement hearing aids
- unwilling or unable to be mailed hearing aids
- co-morbid condition that would preclude their participation as determined by a chart review (e.g., dementia, visual impairment/legal blindeness, substance abuse, etc.)

Materials/Tests:

In addition to RECD and REAR measures, this study will include measures of speech-in-noise abilities and hearing-aid outcomes. These measures are described below:

Client-Oriented Scale of Improvement (COSI; Dillon, James, & Ginis, 1997). The listener nominates up to five listening goals on the COSI. After hearing-aid use, the listener assesses two outcomes for each goal. One outcome is the "degree of change" relative to the patient's unaided experience. Responses are recorded on a categorical scale from 'worse' to 'much better.' The second outcome is the final satisfactory "aided" ability for each goal as measured on a categorical scale from hardy ever (10%) to almost always (95%). The percentage of 'better' and 'much better' responses and the average of the final ability will be calculated across goals. (Session 1—goals established and Session 3—outcomes established—See Procedure Section below) (5 minutes). Device Oriented Subjective Outcome (DOSO) Scale (Cox, Alexander, & Xu, 2009). The questionnaire is comprised of 28 items making up the following six subscales related to listening performance with hearing aids: (1) speech cues, (2) listening effort, (3) pleasantness,(4) quietness, (5) convenience, and (6) use. Responses from 'not at all' (1 point) to tremendously (7 points) are recorded for each item. Higher scores represent better device-oriented subjective outcome. This is a post-only measure (Session 3) (10 minutes).

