Satisfaction with Amplification in Daily Life (SADL) (Cox and Alexander, 1999). The SADL questionnaire has 15 items that examine self-reported hearing-aid satisfaction. The following four subscales are included: (1) positive effect, (2) negative features, (3) personal image, and (4) service and cost. For the current study, item 14 on the service and cost subscale was not used as the Veterans were not charged for the cost of their bilateral hearing aids. The SADL uses a 7-item response scale in 1-unit steps, 1 (poorest) to 7 (highest) for each item, which are averaged for each subscale and total scale score. (Session 3) (5 minutes).

Words-In-Noise (WIN) test uses the NU-6 materials in a six-talker multi-talker babble. The words are presented at 7 signal-to-noise ratios (S/N), 24-dB to 0-dB S/N, in 4-dB decrements. The noise level remains constant and the level of the words varies. Listeners with pure-tone averages ≤25-dB HL will be presented with noise levels at 70-dB SPL and the words will vary from 94- to 70-dB SPL. Listeners with pure-tone averages 25.1- to 40-dB HL will be presented with noise levels at 80-dB SPL and the words will vary from 104- to 80-dB SPL. Listeners with pure-tone averages between 40.1- and 60-dB HL will be presented with noise levels at 90-dB SPL and the words will vary from 114- to 90-dB SPL (following Wilson, 2003; Wilson, Abrams, & Pillon, 2003; Wilson & Burks, 2005). The 50% point on the WIN will be calculated for each ear using the Spearman-Kärber equation (Finney, 1952) in addition to the percent correct performance at each signal-to-noise ratio. (Session 1) (5 minutes).

Procedures.

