Session 1 (Baseline, Pre-Fitting). All testing will be completed separately in each ear for all groups. Otoscopy will be performed and cerumen management completed as needed. The standard audiometric evaluation including air- and bone-conduction pure-tone audiometry; word-recognition in quiet (NU-6 words) and in noise (WIN) will be completed. Tympanometry and aural acoustic reflexes also will be measured. The COSI will be completed to obtain the listening goals of the participant and to facilitate programming needs of the replacement hearing aids (e.g., whether or not manual programs are needed/desired). In addition, an intake form (**Appendix 2**) will be completed for all groups to determine other device options and function (e.g., volume control options such as yes/no or unlinked/linked; removal filament or not; earmold style from previous order form; and tubing length; etc.). If care or use questions arise based on responses on the intake form, then they will be answered during this session. The replacement hearing aids and earmolds will be ordered using the earmold scans on file with the manufacturer provided that the current earmolds from the old hearing aid are a good fit. If not, then ear impressions will be made for replacement earmolds.

For the experimental groups, the tubing length of the current earmolds will be measured carefully so that the replacement earmold tubing can be cut to the same length at the RECD-fitting (Session 2-below). For the Exp-AVGc group, the current earmold vent size will be measured if the actual size is not available on the previous order form. That way, the average RECD values can be corrected for the vent size of the earmold at the RECD-fitting (Session 2).

For the Exp-M group only, RECD values will be obtained separately for each ear with the patient's current earmolds after they have been cleaned and tubing changed as needed. Using the current earmold as opposed to the foam insert will allow venting and tubing characteristics to be incorporated in the RECD-fitting. The RECD measurement protocol will follow the standard clinical protocol and will use the Verifit 2 system. The test box reference microphone will be calibrated. The RECD transducer will be placed on the BTE coupler and the coupler response will be obtained. The probe tube will be inserted 25-27 mm from the antitragal notch in order to ensure placement

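### The between-group REAR level contrasts in Aims 1 and 2 leave differences in hearing loss in the error term; adjusting for Session 1 thresholds is a nearly free gain in precision

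*Combined protocol and SAP*

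**What the plan says.** Data Analysis, Specific Aims 1 and 2, sets out one mixed-model ANOVA: "This analysis will examine differences (in dB SPL) for REAR (actual vs derived using average vs measured RECD) across frequency and ears". It covers both within-group and between-group comparisons, and three of them matter here.

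- Within ear: in situ against derived REAR in the experimental groups.
- Between people, Aim 1: "if the derived REARs in the experimental groups differ from the" in situ REARs of the SoC group.
- Between people, Aim 2: "if coupler-derived REARs using average-corrected or measured RECDs differ". The two RECD methods belong to two different randomised groups.

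Session 3 adds in situ REARs in all groups, also meant for between-group comparison. No covariate is named, and no stratification by hearing loss is described.

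Under Session 2, right and left aids are programmed separately to the NAL-NL2 prescription and checked against target, with a ±3 dB criterion in the SoC group; the experimental fittings are described as similar. Eligibility sets an upper limit only: "no more than a moderate sensorineural hearing loss (defined as < 60 dB HL pure-tone average at 500, 1000, and 2000 Hz AU". Session 1 collects thresholds in every group: "The standard audiometric evaluation including air- and bone-conduction pure-tone audiometry".

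Sample Size takes 2 dB on average across frequency, "and an SD of 2, then 18 participants are needed for each group", and after attrition "then 9 additional subjects will be needed (N = 63) resulting in 21 participants per group".

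**The concern.** A fitted REAR is roughly that ear's own prescribed output plus a fitting deviation. When REAR levels are compared between groups of different people, variation in prescribed output counts as noise. The quantity of interest, the effect of the fitting method, lies in the deviation and is expected to be about 2 dB or less. Spread in hearing loss can therefore widen the intervals for the two contrasts that set the experimental methods against standard care and against each other. Threshold is a main determinant of the prescription and is measured the same way in all groups, but the model does not use it.

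**Working it through.** **Inputs.** From Sample Size: difference 2 dB, SD 2, 18 per group evaluable (21 recruited), alpha .05, power .80. Two-sided testing is assumed. All calculations are at person level, with one value per participant. The SD of 3 and the shares of variance explained (R²) are assumptions.

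**1. The plan's own figure.** For a two-sample t-test with n per group, noncentrality = 2 / (SD × √(2/n)). With n = 18 and SD 2, √(2/18) = 0.333, so noncentrality = 2 / 0.667 = 3.00 on 34 df, and power = 83.0%. At n = 17 power is 80.7% and at n = 16 it is 78.1%, so 18 is sufficient. With all 21 retained, power is 88.5%.

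**2. Which contrast that figure covers.** Other readings also fit 18:

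| Reading at n = 18 | Power |
|---|---|
| Two groups, SD 2 | 83.0% |
| Paired, SD 2 per reading, readings uncorrelated (difference SD 2.83) | 80.7% |
| Paired, difference SD 2 | 97.9% |
| Two-group equivalence, margin 2 dB, SD 2, true difference 0 | about 80% |

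The number alone does not show which was meant.

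**3. Worst case for adjustment.** One covariate costs one degree of freedom (34 to 33). Chance imbalance inflates the variance of the group contrast on average by 1 + 1/(2n − 4) = 1 + 1/32 = 1.031 at n = 18. If threshold explains nothing and SD stays at 2, power averaged over chance imbalance is 81.8% against 83.0% (n = 21: 87.7% against 88.5%).

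**4. Break-even.** Adjustment multiplies the variance by (1 − R²) × 1.031. This is below 1 when R² > 1 − 1/1.031, or about 0.03. The lost degree of freedom changes this very little.

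**5. Possible gain, under assumptions.** With SD 3 and no adjustment, noncentrality at n = 18 is 2 / (3 × 0.333) = 2.00 and power is 49%. Residual SD after adjustment is 3 × √(1 − R²).

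| R² | Residual SD | Power, n = 18 | Power, n = 21 |
|---|---|---|---|
| unadjusted | 3.00 | 49% | 56% |
| 0.25 | 2.60 | 60% | 67% |
| 0.50 | 2.12 | 77% | 84% |

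The adjusted rows include the cost from step 3.

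**6. What cannot be computed.** The documents give neither a between-person SD of REAR level nor a correlation of REAR with threshold. The actual loss without adjustment is therefore unknown.

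**The case against.** The strongest reply is that an unadjusted comparison of randomised groups is valid, so omitting a covariate is a choice and not an error. That stands, and it rules out any reading that the contrasts are biased or their error rate inflated.

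Second, a reader might infer that the trial is underpowered or its sample size wrong. The documents do not support this. The 18 per group reproduces, and low power appears only at SDs assumed by the reviewer. If SD 2 is already the total between-person SD, power is 83%. The 2 dB wording may also concern agreement of in situ with derived REAR in the same ear, where hearing level cancels; the plan nowhere claims 80% power specifically for the between-group level contrasts.

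Third, the evidence for a wide spread of hearing loss is limited. The WIN section says "Listeners with pure-tone averages between 40.1- and 60-dB HL will be presented with noise levels at 90-dB SPL" and gives lower levels for milder losses, but these are presentation rules taken from published procedure and do not describe the expected sample. The case for adjustment needs no wide spread, only that threshold explains more than about 3% of the variance.

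Fourth, each ear yields two REARs: derived then in situ in the experimental arms, and in situ twice in SoC. A group-by-measurement term in the planned model would remove the stable hearing level within each ear. This is correct and useful, but it answers a different question from the level contrasts that the plan names.

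Finally, one might go further and replace the outcome with deviation from target, or demote the derived-REAR contrasts. A precision issue does not justify that. Session 3 in situ REAR is already planned for between-group comparison, and a deviation outcome raises an unsettled question because the experimental targets use arm-specific RECDs.

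**Conclusion.** The point holds as an available improvement in precision. The two between-group level contrasts, and the Session 3 in situ comparison between groups, carry differences in prescribed output in their error term, while a suitable covariate is collected in everyone and left out of the model. The within-ear contrast is not affected. The worst-case cost of adjusting is about 1.2 percentage points of power (83.0% to 81.8% at 18 per group, 2 dB, SD 2). The gain could be much larger, but its size rests on assumed values of SD and R². That the sample size text does not name its contrast or type of SD is secondary: it limits what a reader can conclude about power for these contrasts and does not show that the number is wrong.

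**What to change.** In the planned mixed model, adjust every between-group REAR level contrast for the Session 1 pure-tone threshold at the same ear and frequency, and allow the slope to vary by frequency if needed. This covers experimental derived against SoC in situ, average-corrected against measured RECD, and the Session 3 in situ comparison between groups. Name the covariate before the data are analysed. Outcomes and aims stay as written.

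No new measurement or visit is needed. The statistical cost is the small power loss shown above, with a few more degrees of freedom if slopes differ by frequency. The plan should also say how threshold is assigned at any REAR frequency where none was measured.

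As a clarification only, one sentence in Sample Size could say which contrast the 2 dB refers to, what the SD of 2 is an SD of, and whether the aim is to detect a difference or to show agreement.

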within approximately 2-5 mm from the eardrum. The participant's current earmold (lubricated to ensure a good seal) will be placed in the ear canal and care will be taken not move the probe tube during earmold insertion. The RECD transducer will be coupled to the earmold tubing and the realear response will be obtained. The difference between the coupler and real-ear responses is the measured RECD.

Session 2: The Intervention 'Visit'.

Soc Group Fitting. This group will receive the SoC, 30-minute face-to-face fitting appointment 4-6 weeks after Session 1, the average wait time for a fitting appointment. The right and left hearing aids will be programmed separately to the National Acoustics Laboratory Non-Linear 2 (NAL-NL2) prescription. The REAR of the hearing aids will be verified to the 50-, 65-, and 75-dB SPL prescriptive targets generated by the Verfit 2 system using the speechmap stimulus. The criterion for an appropriate fitting would be ± 3 dB between the output and the prescriptive target from 250 Hz to the frequency in which the unaided threshold crossed the 65-dB SPL target. The Real Ear Saturation Response (RESR) will be measured using an 85-dB swept pure-tone to ensure that the maximum output of the hearing aids does not exceed the predicted uncomfortable loudness levels of the participant. The programming options will be optimized based on the information obtained on the intake form (**Appendix 2**). The participant will be provided with the manufacturer brochure, programming report from the manufacturer software, and the VA Hearing Aid Booklet. Consistent with current SoC, no orientation will be provided.

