Experimental Group Fittings. The participants in the experimental groups will not be present during the fitting. The hearing aids will be fitted in a manner similar to the SoC fitting except the average-corrected (for vent size) RECD (Exp-AVGc Group) or measured RECD from Session 1 (Exp-M group) will be inputted into the Verfit 2 to generate the prescriptive targets and the derived REARs will be obtained following the standard clinical procedure. In short, the tubing of the *replacement* earmold will be cut to length and coupled to each hearing aid. The earmold will be attached to the HA-1 coupler with putty ensuring that the eartip is flush against the opening of coupler and the vent sealed, as is standard with this procedure. The hearing aids will be programmed and the derived REARs will be obtained and verified against the prescription. After programming and verification, the hearing aids will be mailed to the patient along with the manufacturer brochure, programming report from the manufacturer software, and the VA Hearing Aid Booklet within one business day of their receipt from the manufacturer. It is estimated that these experimental fittings will take 15 minutes, or half the time of the SoC fittings. A signature will be required to accept the delivery and the delivery will be tracked.

Two-Day Follow-Up Phone Call. All participants will receive a 2-day follow-up phone call after the hearing-aid fitting. The experimental groups will be phoned after delivery of the hearing aid is confirmed with the delivery receipt. A telephone script (**Appendix 2**) will be used to ask questions about the physical comfort of the device, sound quality, and any other hearing-aid problems or questions.

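### The itemised Aim 2 test compares coupler-derived REARs, which reflects target match and target shift rather than in-ear accuracy; the between-group contrast of in situ minus derived REAR should be the Aim 2 test

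*Combined protocol and SAP*

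**What the plan says.** The opening statement of purpose says that fitting accuracy will be compared. Aim 2 is worded as whether fittings made with measured and with average-corrected RECDs are different; it does not say whether derived or in situ REARs are meant.

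Data Analysis, Specific Aim 1 and 2, states a mixed-model ANOVA of "REAR (actual vs derived using average vs measured RECD) across frequency and ears within and between the groups". It then lists what the analysis will determine:

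- Item (1) covers in situ versus derived REARs in the experimental groups, and derived REARs in those groups versus in situ REARs in the SoC group.
- Item (2), the Aim 2 item, is "if coupler-derived REARs using average-corrected or measured RECDs differ".
- Item (3) breaks off in mid-sentence.

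Session 2, Experimental Group Fittings, describes how derived REARs arise. The average-corrected or measured RECD "will be inputted into the Verfit 2 to generate the prescriptive targets". The earmold is attached to the coupler, "flush against the opening of coupler and the vent sealed". Then "The hearing aids will be programmed and the derived REARs will be obtained and verified against the prescription". The participant is not there. SoC aids are verified in the ear, against "prescriptive targets generated by the Verfit 2 system using the speechmap stimulus", so the SoC group has no derived REAR.

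Session 3 collects in situ REARs in all three groups. These "will allow within and between group comparisons regarding the hearing-aid function and determine the accuracy of the experimental fittings relative to the SoC fittings". The repeated SoC measurements at Sessions 2 and 3 are to show the inherent variability of in situ REARs and "will facilitate interpretation of REAR data when comparing the accuracy of the" in situ and derived REARs in the experimental groups.

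**The concern.** A derived REAR is the quantity that the clinician adjusts until it meets the prescription. Comparing it between Exp-AVGc and Exp-M mostly asks whether two sets of aids were both adjusted to target in the test box. If the two RECD inputs also move the targets, the comparison picks up that shift. With the vent sealed on the coupler, the real vent enters only through the RECD that was keyed in. Nothing in the comparison depends on what reaches the participant's eardrum.

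A non-significant result for item (2) could therefore be reported as the two RECD methods being equally accurate, when it shows only that both reached target on the coupler. A significant result could reflect a target shift rather than a less accurate fitting. The second half of item (1) shares the weakness: setting derived levels against SoC in situ levels uses no in-ear information from the experimental participants.

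**Working it through.** **1. The plan's own sample size.** Inputs from Sample Size: difference 2 dB, SD 2 dB, power 0.80, alpha 0.05 (taken as two-sided). The normal approximation gives n = 2 × (1.960 + 0.842)² × 2² / 2² = 15.7, so 16 per group. The exact two-sample t calculation gives 17. The stated 18 is reproduced within rounding and has exact power 0.830.

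**2. What each contrast measures.** Let e be the entered minus the true RECD, T the target, k the share of e that moves the target (the documents do not give k), f the fitting error and r the retest noise.

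- Derived REAR (Session 2) = T + k·e + f
- In situ REAR (Session 3) = derived REAR − e + r
- D = in situ − derived = −e + r

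With a mean error of 2 dB in Exp-AVGc and none in Exp-M, the expected derived-versus-derived difference is 2k dB. The mean in-ear deviation from T in Exp-AVGc is 2(1 − k) dB in size. As k rises, the itemised contrast grows while the in-ear deviation shrinks. The expected group difference in D is 2 dB in size at every k, so D measures RECD prediction error.

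**3. D is a term of the stated model.** With two groups and two REAR types, the group-by-REAR-type interaction is the two-sample t test on D. In one simulated data set (18 per group), the interaction F was 21.979 and the squared t on D was 21.979. This identity covers the two experimental groups only.

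**4. Power for D at 18 per group, difference 2 dB.** The noncentrality is (2/SD) × √(18/2) = 6/SD, with 34 degrees of freedom and a two-sided test at 0.05.

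| Assumed SD of D (dB) | 6/SD | Power |
|---|---|---|
| 1.5 | 4.0 | 0.973 |
| 2.0 | 3.0 | 0.830 |
| 2.5 | 2.4 | 0.645 |
| 3.0 | 2.0 | 0.493 |

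The plan does not say which quantity its SD of 2 describes. If it is the SD of each REAR and the two are uncorrelated, the SD of D is 2 × √2 = 2.83 dB and power is 0.54.

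**5. Illustration of direction only.** Every SD and k here is assumed: f 1 dB, r 1 dB, e 1.5 dB in Exp-AVGc and 0.75 dB in Exp-M, mean error 2 dB in Exp-AVGc only, 18 per group, 20,000 simulated trials.

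| k | Derived difference 2k (dB) | In-ear deviation 2(1 − k) (dB) | Derived v derived rejects, equal targets | Same, target SD 5 dB | D rejects |
|---|---|---|---|---|---|
| 0 | 0 | 2 | 5% | 5% | 96% |
| 0.25 | 0.5 | 1.5 | 29% | 6% | 96% |
| 0.5 | 1 | 1 | 71% | 9% | 96% |

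Across 54 other combinations of the SDs at k = 0, D rejects in 51% to 97% of trials and derived versus derived in 4% to 6%.

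**6. Why |D| is needed too.** Signed errors can cancel. With mean D of zero in both groups and assumed SDs of D of 4 and 2 dB, the signed comparison rejected in 5.3% of runs and a comparison of |D| in 69.4%.

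**The case against.** The strongest reply is that this is a labelling matter. Item (1) already contrasts in situ with derived REARs within the experimental groups. Session 3 announces between-group accuracy comparisons with the SoC repeat as benchmark, and the ANOVA holds the interaction for the two experimental groups. All of this stands. A reader might infer that the plan never assesses in-ear accuracy, or that its data or model cannot compare it between RECD methods; the documents do not support either reading. But the only complete item for Aim 2 names a different contrast. Finding in situ versus derived significant in one experimental group and not in the other is not a test of the difference between them.

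Further points, each with some force:

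- **Item (3) breaks off.** It may have named the missing contrast. Nothing is inferred from it, and the point is confined to the complete items.
- **The 5% figure.** A reader might infer that derived versus derived can never detect anything. That holds only at k = 0, and the fitting procedure says that the RECD is used to generate targets. At larger k the test does reject, but for target shift.
- **Audiograms.** A reader might infer that audiogram differences bias item (2). Assignment is random, so they are chance noise that lowers power.
- **SoC.** The stated REAR-type factor is not crossed with the SoC group, which has no derived REAR, so the interaction as written does not give the SoC comparison.
- **SoC session.** Session 3 gives context by tying accuracy relative to SoC to that visit's in situ REARs, but item (1) does not say which session's values it uses.

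**Conclusion.** The point holds in limited form and should be fixed. As itemised, the Aim 2 test cannot show which RECD method is more accurate in the ear, because the quantity compared is fixed on the coupler against targets built from the RECD under study. That conclusion follows from the fitting procedure and does not depend on the simulation. The valid within-group contrast limits the damage, and no data are lost. What remains is the risk that a null on item (2) is read as equal accuracy, with the term that decides Aim 2 left open until the data are seen.

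The planned size may suit the better test: 83% power for a 2 dB difference in D if the SD of D is 2 dB, but 97% to 49% over an SD of 1.5 to 3 dB. Confidence is medium, because item (3) is incomplete and neither k nor the SD of D is given.

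**What to change.** Amend the analysis wording for Aims 1 and 2:

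- **(a)** Make the Aim 2 test the Exp-AVGc versus Exp-M comparison of D = Session 3 in situ REAR minus Session 2 derived REAR (the group-by-REAR-type interaction), described as a test of RECD prediction error. Keep derived versus derived as a description of target match only.
- **(b)** For the comparison with SoC, set each experimental group's D against the SoC Session 3 minus Session 2 in situ difference, coding session in place of REAR type. State which SoC session is used wherever SoC in situ levels are compared.
- **(c)** Report |D| alongside D.

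The within-group contrast in item (1) stays as it is. The cost is a few sentences and a little more analysis work. No visit or measurement is added, because Session 2 and Session 3 REARs are already planned in every group.
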